The power analyses for Primary Hypothesis 1 were calculated following the recommendations of Liu and Wu [16]. The analysis was based on a corrected alpha of .025 (.05/2 primary outcomes), a compound symmetry covariance structure, an estimated abstinence rate of 25% in the SC condition (based on data from our prior study), a correlation between observations on the same patient of .50, and assuming 20% attrition at the final time point. We identified two primary subgroup analyses to be performed: (1) setting [recently discharged inpatients (IP, n = 400) vs. patients presenting for outpatient treatment (OP, n = 400)] and (2) type of opioid [heroin (n = 534) vs. prescription (n = 266)]. For the smallest subgroup (patients primarily using prescription opioids: n = 266; 133 per condition), we will have 80% power to detect an approximately 15% difference in abstinence rates between the conditions (i.e., 25% in control vs. 40% in experimental; OR = 2.0). This projected difference is conservative and based only on the repeatedly demonstrated, similarly scaled differences contingency management yields when compared to standard treatment conditions [17-21]. The smallest detectable differences for the remaining subgroups and the overall sample are as follows using the same specifications: (1) patients recruited from IP setting (n = 400): 12%, OR = 1.8, (2) patients recruited from OP setting (n = 400): 12%, OR = 1.8, (3) patients primarily using heroin (n = 534): 9%, OR = 1.6, and (4) the overall sample (n = 800): 8%, OR = 1.5. The power analyses for Primary Hypothesis 2 were calculated following the recommendations of Lakatos [22]. The analysis was based on a corrected alpha of .025, no attrition as chart data will be available for all patients, and estimated dropout rate of 60% in the SC condition [23]. For the smallest subgroup (patients primarily using prescription opioids: n = 266; 133 per condition), we will have 80% power to detect a hazard ratio of .59 which corresponds to a difference in survival rates of approximately 18% between the two conditions. The smallest detectable hazard ratio for the remaining subgroups and overall sample are as follows using the same specifications: (1) patients recruited from IP setting (n = 400): HR = .65, 15% difference in survival (2) patients recruited from OP setting (n = 400): HR = .65 , 15%

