The measures listed below are collected for research purposes only and will not become part of patients' medical records. These measures will be stored separately from those collected as part of the medical record, and only TRI researchers will be able to link this data to the patient.

Weekly during Weeks 1 through 6, Pilot Study Only:

Weekly Timeline Followback (TLFB): The TLFB [42] is a structured interview which helps patients recall their substance use to reflect a specified period. Patients are presented with a calendar representing the past 7 days, and the interviewer helps the patient anchor the calendar with memorable events to reconstruct their use (dates, amounts) over the designated period.

Baseline and Follow-up Instruments (administered at Baseline, 3-, 6-, 9-, 12-, 15-, and 18 month follow-ups):

Urine testing: On-site urine drug testing kits (ACON International) rapidly (5-minute) test for cocaine, opiates, amphetamines, methamphetamines, benzodiazepines, cannabis, barbiturates, PCP, and alcohol. Urine testing will be administered at all follow-ups to capture very recent use (i.e. past 3 days).

Hair follicle testing: Hair follicle samples will be sent to an accredited laboratory for testing. Samples generally provide a 90-day window of use, and will be tested for opiates, cocaine, amphetamines, methamphetamines, ecstasy, marijuana, and PCP. If a hair sample of 1.5 inches cannot be provided, urine sampling only will be performed.

Non-Study Medical and Other Services (NSMOS): This questionnaire was adapted from the Treatment Services Review [43,44] for patients in medical settings. The NSMOS counts substance abuse treatment, medical services, visits to medical offices, hospitalizations, and emergency room visits received that were not a part of the assigned treatment.

FQHC / SUD Treatment Program Case Review: Chart review will verify patient self-report of treatment engagement. We will obtain the first version of this data by pulling payment data from funders. We will resolve inconsistencies between patient report and billing data through chart review.

Texas Christian University Treatment Engagement (TCU ENGForm): The TCU ENGForm [45] measures patient therapeutic engagement in and satisfaction with substance abuse treatment. It includes 36 items from four scales representing Treatment Participation, Treatment Satisfaction, Counseling Rapport, and Peer Support, and it takes approximately 10 minutes to complete.

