For patients who consent to screening, an RA or BHC will administer the ASAM Criteria Software interview to determine if they meet DSM-V criteria for a Moderate to Severe OUD diagnosis with ≥ 4 symptoms and opioid use within the past month. Patients meeting criteria must also affirm that they are not currently engaged in primary care (no provider, or no PC contact in the past year), and be willing to receive care at the participating FQHC. Eligible patients will then be invited to complete informed consent with an RA.

Inclusion and Exclusion Criteria

Inclusion Criteria: 1) patient is 18 years or older, 2a) they meet the criteria for Level 1 care, i.e., outpatient treatment, as defined by the ASAM Criteria, and determined for the patient’s needs according to the decision engine built into the ASAM Criteria Software, or 2b) they meet criteria for Level 2 care (Level 2.0), i.e., intensive outpatient program..

Exclusion Criteria: (a) the medical practitioner or BHC overrule these criteria because medical and psychiatric complications exist that would contraindicate research participation; (b) they have an ASAM level of care higher than 2.0, (c) the patient reports plans to leave the area (i.e. Philadelphia or Washington DC greater metropolitan area) within the next 6 months; (d) the patient is not English-speaking; (e) if the patient is unable to provide valid informed consent by correctly describing the key components of consent to the RA.

Informed Consent

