Primary Hypothesis 1: Clients in the PATH condition will demonstrate higher rates of confirmed substance abstinence (hair and UA verified) during treatment and at follow-up than clients in the SC condition. Confirmed abstinence is the “gold standard” of direct clinical outcomes in SUD research. A mixed effects logistic regression model [2,3] will be used to compare the binary outcome of hair and urinalysis-confirmed abstinence in the two treatment conditions at months 3, 6, 9, 12, 15, and 18. Mixed effects models have advantages of traditional repeated measures approaches in that they allow for missing observations, accommodate measurements made at different time points, provide flexibility in modeling the variance-covariance matrix, and permit the estimation of both group and random patient-specific effects. The model will include terms for treatment condition, time, and their interaction, and the binary baseline abstinence variable along with any other necessary covariates. We will follow the recommendations of Varadhan and Seeger [4] to test heterogeneity of treatment effect (HTE). We have identified two primary subgroup analyses to be performed: (1) setting [IP (n = 400) vs. OP (n = 400)] and (2) type of opioid [heroin (n = 534) vs. prescription (n = 266)]. We will use similar mixed effects logistic regression models (described above) that will additionally include terms for the specific subgroup variable and its interaction with treatment condition. In the event that the interaction is significant, the treatment effect will be estimated separately at each level of the categorical variable that is used to define the subgroups. In addition, we will conduct an *exploratory* subgroup analysis for medication type (agonist vs. antagonist/drug free). We anticipate simple time trends (e.g., linear or quadratic) for the mixed effects models; however, we will use linear spline models in the event complex time trends are observed, such as non-linear trends that cannot be approximated by simple polynomials in time [2]. These analyses will be performed using PROC GLIMMIX.

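### The only baseline covariate named for the abstinence model says little about baseline drug use: it should be non-abstinent for everyone with usable hair, and would vary mainly through missed detection

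*SAP*

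**What the plan says.** The SAP (Primary Hypothesis 1) fits a mixed effects logistic model to abstinence confirmed by hair and urine at six visits. The terms are treatment, time, their interaction, and "the binary baseline abstinence variable along with any other necessary covariates". Baseline abstinence has no definition of its own, so the natural reading is the baseline value of the outcome.

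The protocol supplies the rest:

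- Item 9 (Screening): the ASAM Criteria interview must show moderate to severe OUD and "opioid use within the past month".
- Item 6 (Client Baseline Procedures): hair and urine are both collected at baseline.
- Item 7 (Hair follicle testing): "Samples generally provide a 90-day window of use". The fallback is also there: "If a hair sample of 1.5 inches cannot be provided, urine sampling only will be performed". Urine is described as covering about the past 3 days.
- Item 5: the planned sample is 400 recently discharged inpatients and 400 outpatients.

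Two other statements bear on the point. The SAP's opening paragraph says that the full-sample primary analyses will carry no covariates, which conflicts with the Primary Hypothesis 1 model. And the past-month rule is in the screening text but not in the formal list in item 9, which begins "Inclusion Criteria: 1) patient is 18 years or older, 2a) they meet the criteria for Level 1 care" and covers only age and level of care.

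**The concern.** A baseline covariate earns its place by separating patients who start in different states. This one is set against an entry rule that nearly fixes its value. A participant who used opioids in the past month and gives hair with a 90-day window should be coded non-abstinent, whether just discharged from an inpatient stay or still using.

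The main route to an abstinent code is a sample that missed known use. The clearest case is a participant without enough hair whose urine is negative, for example after inpatient detoxification. That code records which test was possible and where the patient had just been, not abstinence over the outcome's window.

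At stake is precision, and control of a chance imbalance in starting state. Randomisation is stratified by new or existing patient and by site (protocol item 6), not by inpatient or outpatient origin. Setting enters only the subgroup models.

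**Working it through.** **1. The plan's own figure, and whether it uses the covariate.** Inputs from the SAP (Power for the Primary Hypotheses): alpha .025 (taken as two-sided), 80% power, 25% v 40%, within-patient correlation .50, 20% attrition. Six visits come from Primary Hypothesis 1.

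- Two-proportion sample size: 185 per condition.
- Factor for averaging six correlated visits: (1 + 5 × .5)/6 = .5833.
- 185 × .5833 / .8 = 135 per condition, against 133 stated. Power at 133 is 79.6%.

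The stated figure reproduces closely, and the method has no term for a baseline covariate. The stated power therefore does not rest on it.

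**2. How often could the covariate read abstinent?** The documents do not give the share without usable hair (h) or the urine-negative share among them (u). If hair detects all past-month use, prevalence q = h × u:

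| h (assumed) | q for u = 20% to 80% (assumed) |
|---|---|
| 0% | 0% (constant) |
| 5% | 1% to 4% |
| 10% | 2% to 8% |
| 20% | 4% to 16% |
| 40% | 8% to 32% |

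At 1% to 2% of 800, the abstinent level holds 8 to 16 patients. Missed detection in hair would add to q. Both panels list opiates, and the documents do not say whether they cover every prescription opioid used by the 266 patients expected to use mainly these.

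**3. How much could it explain?** The variance of a patient's time-averaged outcome is .25 × .75 × .5833 = .1094. A binary covariate with prevalence q and outcome difference d explains q(1 − q)d²/.1094. The values of d are assumptions.

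| q | d = .2 | d = .4 |
|---|---|---|
| 0% | 0% | 0% |
| 2% | 0.7% | 2.9% |
| 10% | 3.3% | 13% |
| 20% | 5.9% | 23% |

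A second approximation, using baseline-outcome odds ratios of 2 to 8, gives 0.4% to 4.1% at q = 2% and 2.9% to 29% at q = 20%. The answer turns on h and u. At the high end the predictive strength could itself be partly a test artefact, because a participant without hair at baseline may also be urine-only at follow-up, where abstinence is judged on the shorter window.

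**4. What a graded measure might be worth.** Let r be its correlation with time-averaged abstinence (not in the documents). Starting from 80%, power = Φ(3.083/√(1 − r²) − 2.241), where 3.083 = 2.241 + .842. The equivalent increase in sample size is 1/(1 − r²).

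| r (assumed) | Sample-size factor | Power |
|---|---|---|
| .2 | 1.04 | 81.7% |
| .3 | 1.10 | 83.9% |
| .4 | 1.19 | 86.9% |

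Steps 3 and 4 are linear approximations, not a fit of the planned mixed logistic model.

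**The case against.** The strongest reply is that a weak covariate does no harm. It leaves the randomised comparison unbiased, and if constant it drops out. The SAP's opening paragraph deliberately declines covariates in the full-sample analyses. The plan also checks baseline balance, allows other necessary covariates, models setting as a prespecified subgroup and examines OUD severity under Heterogeneity of treatment effects. With 400 per condition a large chance imbalance is unlikely. The 80% starting point applies in the full sample only near its 8-point minimum detectable difference. At the projected 15 points, scaling from 133 to 400 per condition gives Φ(3.083 × √(400/133) − 2.241), about 99.9%.

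All of this limits the size of the point. It does not rescue the variable, since the SAP chose to adjust for baseline status and named a measure that cannot do it well. The opening paragraph does not settle the matter either, because it contradicts the model specified for the same analysis.

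Three stronger readings are tempting, and the documents support none of them:

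- A reader might infer that the covariate is constant across the whole sample by design. The urine-only fallback prevents that conclusion, and recently discharged inpatients could well be urine-negative.
- A reader might infer a ceiling of about 3% on what it explains. That holds only at an assumed prevalence of 2% or less; step 3 reaches 13% to 23% at 10% to 20%.
- A reader might infer that the primary comparison is biased or the stated power wrong because of this covariate. Neither follows.

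It is also fair that baseline urine keeps the 3-day window. But it applies one window to everyone and claims no more than recent use.

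**Conclusion.** The point holds in a limited form. Among participants with usable hair who meet the past-month rule, baseline abstinence should not vary. Elsewhere it varies mainly through missed detection, mixing a 90-day and a 3-day window. It therefore carries little valid information about baseline drug use, whatever its prevalence.

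This rests on two readings: that baseline abstinence is defined as the outcome is, and that the past-month rule in the screening text is enforced although the formal inclusion list omits it.

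The cost is lost precision and an unadjusted chance imbalance in starting state, not bias. The gain from 80% to about 82%, 84% or 87% illustrates correlations of .2, .3 and .4; the documents cannot confirm any of these.

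**What to change.** In the SAP, Primary Hypothesis 1, replace "the binary baseline abstinence variable along with any other necessary covariates" with named pre-randomisation measures that can vary under the entry rule: *the baseline urine result, coded on the same substances as the outcome, and the baseline ASAM Criteria self-reported drug-use severity score*. Closing the list also removes the open-ended choice of further covariates. Use days of use only if the ASAM interview yields it, because the Timeline Followback is listed for the pilot alone.

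In the same edit, amend the opening paragraph's statement that full-sample primary analyses will not include covariates, so that the two places agree.

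The cost is SAP wording only. Both measures are already collected: the ASAM interview determines eligibility, and the protocol describes the baseline urine sample ahead of random assignment. No new data, visits or patients are needed.

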Primary Hypothesis 2: Clients in the PATH condition will demonstrate greater retention in treatment than clients in the SC condition. Retention is widely considered the leading proxy for clinical effectiveness in SUD treatment. A Cox proportional hazards survival analysis [5,6] will be used to determine whether the rate of dropout differs between the two treatment conditions. The analysis will account for right-censored data as some participants may not experience the event (i.e., treatment dropout, defined as absence from treatment for 30 days) during the period of observation. The analysis will include any necessary covariates. To establish the HTE for this outcome, the survival analysis will be repeated for each primary and exploratory subgroup identified above. Models will include a term for the subgroup variable and its interaction with treatment condition. Again, if the interaction term is significant, the treatment effect will be estimated separately at each level of the categorical variable that is used to define the subgroups. We anticipate that the proportional hazard assumption will be met as we expect the typical pattern of dropout in both groups (i.e., high hazard early, low hazard late). We will conduct standard residual-based analyses to evaluate proportionality and, in the event that the

proportional hazard assumption is violated, we will use extended Cox models that include a time-dependent covariate to model the non-proportionality [7]. The analyses will be performed using PROC PHREG.

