Power for the Primary Hypotheses. Power analyses were calculated for the primary hypotheses described above. The power analyses for Primary Hypothesis 1 were calculated following the recommendations of Liu and Wu [8]. The analysis was based on a corrected alpha of .025 (.05/2 primary outcomes), a compound symmetry covariance structure, an estimated abstinence rate of 25% in the SC condition (based on data from our prior study), a correlation between observations on the same patient of .50, and assuming 20% attrition at the final time point. For the smallest subgroup (patients primarily using prescription opioids: $n = 266$; 133 per condition), we will have 80% power to detect an approximately 15% difference in abstinence rates between the conditions (i.e., 25% in control vs. 40% in experimental; OR = 2.0). This projected difference is conservative and based only on the repeatedly demonstrated, similarly scaled differences contingency management yields when compared to standard treatment conditions [9-13]. The smallest detectable differences for the remaining subgroups and the overall sample are as follows using the same specifications: (1) patients recruited from IP setting ($n = 400$): 12%, OR = 1.8, (2) patients recruited from OP setting ($n = 400$): 12%, OR = 1.8, (3) patients primarily using heroin ($n = 534$): 9%, OR = 1.6, and (4) the overall sample ($n = 800$): 8%, OR = 1.5. The power analyses for Primary Hypothesis 2 were calculated following the recommendations of Lakatos [14]. The analysis was based on a corrected alpha of .025, no attrition as chart data will be available for all patients, and estimated dropout rate of 60% in the SC condition [15]. For the smallest subgroup (patients primarily using prescription opioids: $n = 266$; 133 per condition), we will have 80% power to detect a hazard ratio of .59 which corresponds to a difference in survival rates of approximately 18% between the two conditions. The smallest detectable hazard ratio for the remaining subgroups and overall sample are as follows using the same specifications: (1) patients recruited from IP setting ($n = 400$): HR = .65, 15% difference in survival (2) patients recruited from OP setting ($n = 400$): HR = .65, 15% difference in survival (3) patients primarily using heroin ($n = 534$): HR = .69, 13% difference in survival, and (4) the overall sample ($n = 800$): HR = .74, 10% difference in survival. We have chosen to use an alpha level that corrects for the number of primary hypotheses rather than the number of subgroup analyses as the latter approach would substantially increase the likelihood of making a type 2 error [4,16].

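### The abstinence detectable differences for the subgroups do not share one specification, and the stated 80% subgroup power does not describe the interaction test that comes first

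*SAP*

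**What the plan says.** **Power.** Protocol item 5 and the SAP section Power for the Primary Hypotheses carry the same figures. For abstinence they assume alpha .025, 25% abstinence in SC, compound symmetry, and "a correlation between observations on the same patient of .50, and assuming 20% attrition at the final time point". For prescription-opioid users (133 per condition), "we will have 80% power to detect an approximately 15% difference in abstinence rates between the conditions", with OR 2.0. The other rows are introduced by "The smallest detectable differences for the remaining subgroups and the overall sample are as follows using the same specifications". They are IP and OP (n = 400 each) 12%, OR 1.8; heroin, given as "patients primarily using heroin (n = 534): 9%, OR = 1.6"; and overall (n = 800) 8%, OR 1.5. On multiplicity: "We have chosen to use an alpha level that corrects for the number of primary hypotheses rather than the number of subgroup analyses".

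**Analysis.** Under Primary Hypothesis 1 the SAP adds the subgroup and its interaction with condition to the mixed logistic model, then says: "In the event that the interaction is significant, the treatment effect will be estimated separately at each level". Under Primary Hypothesis 2 it says that "the survival analysis will be repeated for each primary and exploratory subgroup identified above", but goes on to describe an interaction model and ends: "Again, if the interaction term is significant, the treatment effect will be estimated separately at each level". The SAP section Heterogeneity of treatment effects applies the same rule to psychiatric severity, OUD severity and housing. None of these places says what is reported when the interaction is not significant. Neither document gives power or a detectable size for an interaction.

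**The concern.** There are two separate issues.

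1. With everything else held fixed, a detectable difference shrinks roughly with the square root of n. Scaling the prescription row to the heroin sample gives 15 × √(266/534) = 10.6 points. Scaling the IP/OP row gives 12 × √(400/534) = 10.4. The stated value is 9. At least one row therefore comes from a different calculation, and a reader cannot tell how much loss the abstinence power allows for.

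2. The 80% subgroup figures concern PATH against SC inside one level. The first subgroup test to be run asks whether the effect differs between levels, which is a harder question. A reader with only the 80% figures could take a null interaction as an adequately powered finding of no heterogeneity. The written plan also makes no provision for level estimates in that case.

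**Working it through.** **Inputs.** From the power section: alpha .025, power .80, SC rate .25, within-patient correlation .50, 20% attrition and the subgroup sizes. From Primary Hypothesis 1: six visits. Two-sided testing is assumed because the power section does not state it. Then (2.241 + 0.842)² = 9.505.

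**Formula.** For a time-averaged difference d, with p = .25 + d and n/2 patients per arm:

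d² = 9.505 × F × [.1875 + p(1 − p)] / (n/2)

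Visits, correlation and attrition enter only through the variance factor F:
- no loss: F = (1 + 5 × .5)/6 = .583
- 20% lost at the last visit only: F = 1/(.8 × 6/3.5 + .2 × 5/3) = .587
- loss accruing evenly from visit 2 to 20% at visit 6: F = .604
- flat 20% loss at every visit: F = .583/.8 = .729

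**Reproducing the stated rows** (points, OR):

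| | n = 266 | n = 400 | n = 534 | n = 800 |
|---|---|---|---|---|
| Stated | 15, 2.0 | 12, 1.8 | 9, 1.6 | 8, 1.5 |
| Flat 20% | 14.9, 1.99 | 12.1, 1.77 | 10.4, 1.64 | 8.4, 1.51 |
| Accruing | 13.5, 1.88 | 11.0, 1.68 | 9.4, 1.58 | 7.7, 1.45 |
| Last visit only | 13.3, 1.87 | 10.8, 1.67 | 9.3, 1.57 | 7.5, 1.45 |

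Flat loss reproduces everything except the heroin 9%. The other two patterns reproduce heroin but not the 15% or the 12%.

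**Rounding.** Solve for F at the edge of each rounding interval:
- 15% needs at least 14.5 points: F ≥ 133 × .145² / [9.505 × (.1875 + .2390)] = .690
- 12% needs at least 11.5 points: F ≥ 200 × .115² / [9.505 × (.1875 + .2318)] = .664
- heroin 9% allows at most 9.5 points: F ≤ 267 × .095² / [9.505 × (.1875 + .2260)] = .613

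No F satisfies all three, so no single attrition pattern, correlation or number of visits does. A different alpha or sidedness would rescale every row alike and leave the conflict in place. The other seven figures (15%, 12%, 8% and the four ORs) share F from .702 to .741, where heroin is 10.2 to 10.5 points. The heroin OR does not decide the matter: ORs of 1.55 to 1.65 correspond to 9.1 to 10.5 points.

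**Power at 9 points in heroin users.** Under flat loss the SE is √[.729 × (.1875 + .2244)/267] = .0335. Then z = .09/.0335 = 2.68, and power is Φ(2.68 − 2.24) = 67%. Under last-visit loss it is 77%.

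**Retention.** The log-rank power at the stated hazard ratios is 79.6%, 81.0%, 81.4% and 81.7% for n = 266, 400, 534 and 800. The row inconsistency is confined to abstinence.

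**Interaction power, abstinence.** This uses two-sided .025, the log-odds scale and no covariates. The variance is the sum over four arms of F / [p(1 − p) × arm size]. The effect in the other level is an assumption, since the documents give none.
- Opioid type, 15 points in prescription users and 0 in heroin users: log ratio of ORs .693, variance F × .1114. Flat loss: SE .285, z = 2.43, power 58%. No loss: SE .255, z = 2.72, power 68%.
- Setting, 12 points in one level and 0 in the other: log ratio .566, variance F × .1014. Flat loss: SE .272, z = 2.08, power 44%. No loss: SE .243, z = 2.33, power 53%.
- If the other level gains 8 points: 12–15% (opioid type) and 6–7% (setting).
- Detectable with 80% power, no effect in the other level: ratio of ORs 2.2–2.4 for opioid type (17–19 points in prescription users) and 2.1–2.3 for setting (16–18 points).

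**Interaction power, retention.** Events are .6 × n/2 in SC and (1 − .4^HR) × n/2 in PATH, and the variance is the sum of 1/events. HR .59 against 1 gives 62%, and .65 against 1 gives 51%. If the other level has HR .74, these fall to 12% and 6%. With 80% power the detectable values against HR 1 are .52 (opioid type) and .55 (setting).

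**The case against.** **On the rows.** A reader might infer that the heroin row overstates what that subgroup can detect. The documents do not support that without a condition. Their wording puts the 20% loss at the last assessment, and with loss at, or accruing to, that visit the heroin 9% and OR 1.6 are right. The prescription and IP/OP rows are then conservative. Flat loss is inferred only because it fits more of the figures. What stands is that the rows cannot share one specification.

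**On the interaction.** A reader might also infer that the SAP claims 80% power for heterogeneity, or forbids level estimates without a significant interaction. It does neither. The figures are labelled as differences between conditions, the rule does not say that estimates are given only then, and the fitted model already yields level effects. The retention text can be read as providing them. Testing the interaction first is sound protection against spurious subgroup claims. The natural reading of the multiplicity sentence is that .025 applies to these tests. This part is therefore a gap in reporting rather than an arithmetic error.

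The interaction powers also depend on assumed effects and leave out covariates, although the planned model includes baseline abstinence. If covariates cut the variance by 10–20% (an assumption), the one-level-only scenarios rise to 63–79% and 48–64%, still below 80%.

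**Conclusion.** The abstinence power rows are inconsistent as written. The 15%, 12% and 9% need F of at least .69, at least .66 and at most .61. The discrepancy is about one point in heroin users under flat loss, or one to two points in the prescription and IP/OP rows under last-visit loss. The documents do not settle which was used. This result does not depend on sidedness or the number of visits.

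Separately, no power is given for the interaction test that precedes the planned level estimates. Under the assumption most favourable among those shown, no effect at all in the other level, it is about 58–68% for opioid type and 44–53% for setting. It is far lower if both levels benefit. This is an omission worth closing, not a false claim. Neither issue touches N = 800 or the full-sample tests.

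**What to change.** 1. Recompute all four abstinence rows on one stated attrition pattern, in the SAP and in protocol item 5, and correct whichever change. Under flat 20% loss only heroin changes, from 9% to 10%, with OR 1.6 unchanged. Under loss at the final visit only, the rows become 13%, 11%, 9% and 8%, with ORs 1.9, 1.7, 1.6 and 1.4.
2. Report the PATH–SC effect with a 97.5% CI at each level of setting and opioid type, for both primary outcomes, whatever the interaction p-value. Do the same for psychiatric severity, OUD severity and housing. Keep the interaction test as the only evidence for heterogeneity, and word level estimates without a significant interaction as descriptive.
3. State that the 80% figures do not apply to the interaction test. Give its detectable size at .025 together with the effect assumed in the other level.

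The cost is wording and a few more estimates to report, with no change to sample size or conduct. The downside is that some stated figures may become less favourable.
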